6.4 Missing Data

There will be no imputation for missing data, unless otherwise specified. Missing data shall be presented in participant listings as either “-” (unknown or not evaluated) or “N/A” (not applicable), with the corresponding definition in the footnotes. Missing descriptive statistics, or probability values (p-values), which cannot be estimated shall be presented as “-”.

For inclusion in concomitant medication and AE tables, incomplete start and stop dates on the eCRF will be imputed as follows:

- If the stop date is incomplete, the following rules will be applied:
 - Missing day: Assume the last day of the month
 - Missing day and month: Assume the last day of the year
 - Missing day, month, and year: Assume that the event/medication is continuing
 - In the case of the death of a participant, and if the imputed end date is after the date of death, the end date will be imputed as the date of death
- If the stop date is incomplete, imputed end date will be used instead of reported end date
- If the start date is incomplete, the following rules will be applied:
 - Missing day: Assume the first day of the month; however, if the partial date and the date of first study drug administration lie within the same month and year and the date of first study drug administration is not after the stop date of the event/medication, set to the date of study drug administration. Otherwise, set to the stop date of the event/medication.

This document is confidential.

- Missing day and month: Assume January 1st; however, if the partial date and the date of first study drug administration lie within the same year and the date of first study drug administration is not after the stop date of the event/medication, set to the date of first study drug administration. Otherwise, set them to stop date of the event/medication.
- Missing day, month, and year: Assume date of first study drug administration if it is not after the stop date for the event/medication. Otherwise, set them to stop date for the event/medication.

In the case of withdrawal of consent, all data from participants who withdraw from the study will be included in all summaries up to the time of withdrawal. For all other withdrawals, all data captured will be included in the safety summaries.

For PK analysis, only observed concentration data will be used in the data analysis except for concentration values below the lower limit of quantification (BLQ). No attempt will be made to extrapolate or interpolate estimates for missing data.

7. Study Population

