8.6 Assessment of Food Effect

To assess the food effect on ATH-399A exposure in Part 1b, the values of AUC_{0-t} , $AUC_{0-\infty}$, and C_{max} calculated for the two diet regimens (fed and fasted) will be evaluated by ANOVA, with terms for sequence, period, and treatment as fixed effects and participant within sequence as a random effect. The exposure measurements ($AUCs$ and C_{max}) will be natural log-transformed prior to analysis. The model will be fitted using restricted maximum likelihood and the Kenward-Roger degrees of freedom approximation. [Error! Bookmark not defined.](#)

The 90% CI for the ratio of the geometric means for AUC_{0-t} , $AUC_{0-\infty}$, and C_{max} obtained between the fed and fasted conditions will be calculated. The absence of a food effect will be concluded when the 90% CI for the ratio of means (geometric means based on log transformed data) of fed and fasted conditions fall within 80% - 125% for AUC_{0-t} , $AUC_{0-\infty}$, and C_{max} .

The SAS code for the analysis model for ANOVA will follow the format given below (using the Mixed Procedure to fit the linear regression). The input variables, datasets, and labels are depicted in italicized red text and have been given generic names.

```
proc mixed data= dataset;
  class participant treatment sequence period;
  model var = treatment sequence period / solution ddfm= KR;
  random participant(sequence);
  lsmeans treatment / cl alpha= 0.1;
  estimate 'fed vs fasting' treatment 1 -1 / cl alpha= 0.1;
  ods output estimates = estimates covparms = covparms;
run;
```

Intra- and inter-participant CV% will also be estimated.

9. Pharmacodynamic (PD) Analyses

There will be no PD analyses for this study.

This document is confidential.

10. Safety

Safety and tolerability analysis will be performed for all participants in the safety population. No inferential statistical analysis of safety data is planned. For Parts 1a and 2, summary tables will be presented by dose (study drug and placebo) and by study drug overall. For Part 1b, summary tables will be presented by treatment and overall.

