10.2 Adverse Events (AEs)

AEs will be coded using the latest version of the MedDRA. Output data will include the MedDRA version used in the study. AEs will be grouped by SOC and PT and summarized by actual treatment. The summary tables will present the number and percentage of total participants and number of events by SOC and by PT.

All AE summaries will be restricted to treatment-emergent AEs (TEAEs), defined as AEs that commence on or after the time of first study drug administration. Any AE that first occurs pre-dose but worsens in intensity after the first study drug administration will also be considered a TEAE. AEs without an onset date or time, or AEs with an onset date of the date of first study drug administration but without an onset time, will be defined as treatment-emergent, unless an incomplete date (e.g., month and year) clearly indicates that the event started prior to administration of first study drug, or the AE stop date indicates that the event started and stopped prior to administration of first study drug.

TEAEs will be attributed to the last treatment administered. TEAEs continuing after dosing in the next treatment period will be evaluated on a case-by-case basis.

The number and percentage of participants experiencing TEAEs and the number of TEAEs will be tabulated. Participants who experience the same TEAE (in terms of MedDRA PT) more than once will only be counted once per treatment or period, however, the total number of events will be counted per category. This also applies to sub-categories displayed in the summaries.

The following summaries will be presented:

- Overall summary of TEAEs
- TEAEs by SOC and PT
- TEAEs by SOC, PT, and intensity
- TEAEs by SOC, PT, and relationship to study drug
- Serious TEAEs by SOC and PT

The Investigator will make an assessment of intensity for each AE and SAE reported during the study per Common Terminology Criteria for Adverse Events (CTCAE) v5.0 grading criteria:

This document is confidential.

- Grade 1: Mild, asymptomatic or mild symptoms; clinical or diagnostic observations only; treatment not indicated.
- Grade 2: Moderate, minimal, local, or non-invasive treatment indicated; limiting age-appropriate instrumental activities of daily life.
- Grade 3: Severe or medically significant but not immediately life-threatening: hospitalization or prolongation of hospitalization indicated; disabling; limiting self-care activities of daily life.

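### SAP 6.4 anchors partial AE onset dates to the first dose, so in the Part 1b crossover most Period 2 events with a missing onset day are dated to Period 1

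*SAP*

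**What the plan says.** SAP 6.4 opens its date rules with "For inclusion in concomitant medication and AE tables, incomplete start and stop dates on the eCRF will be imputed as follows". It does not distinguish study parts.

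- **Missing onset day.** The default and its exception read "Assume the first day of the month; however, if the partial date and the date of first study drug administration lie within the same month" (the calendar year must match too). If the first dose is also not after the stop date, the onset is "set to the date of study drug administration. Otherwise, set to the stop date of the event/medication". The target omits the word 'first', but the condition names the first dose, and so do the two parallel rules.
- **Missing day and month.** The construction is the same, with 1 January as the default and the year as the match.
- **Fully missing date.** "Missing day, month, and year: Assume date of first study drug administration if it is not after the stop date for the event/medication"; failing that, the stop date.

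SAP 10.2 then says "TEAEs will be attributed to the last treatment administered", followed directly by "TEAEs continuing after dosing in the next treatment period will be evaluated on a case-by-case basis". The opening of SAP section 10 says "For Part 1b, summary tables will be presented by treatment and overall". AE incidence is part of the Part 1b primary endpoint (SAP 4.2.1).

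Protocol 7.1.2 gives Part 1b about 12 participants, two doses in sequence AB or BA, and a washout of at least 7 days that may be adjusted on Part 1a data.

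**The concern.** There are two defects in the same rule.

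First, the rule knows only one dose. In Parts 1a and 2 that does no harm of this kind, because nobody changes treatment. In Part 1b, a Period 2 event reported with month and year only is usually pulled back to the Period 1 dose, under the opposite food condition.

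Second, the scope of 'Otherwise' is unclear. Read literally, the exception and the closing clause together cover every case, so the first-of-month and 1 January defaults are never used. An event whose month differs from that of the first dose then starts on its own stop date. An ongoing event has no stop date, so the rule returns nothing. Read as nested within the same-month case, the defaults survive, but the Period 2 problem grows. Two programmers could code this differently.

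At stake is the fed versus fasted AE table, in a part with about 12 participants and no placebo.

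**Working it through.** The documents give no figure on this point, so none can be reproduced.

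**Inputs from the documents.** The gap g between doses is at least 7 days (Protocol 7.1.2). Table 2, footnote 3, puts follow-up 7 days after the last dose, from Day 16. Dose 2 is then on Day 9, so g = 8.

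**Assumptions.** Dose 1 is equally likely on each of 366 consecutive dates, which contain 12 month starts. Period 2 onset falls with equal chance o = 0 to 7 days after dose 2 (mean 3.5). The onset day is missing; month, year and stop date are known.

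**Example.** Doses are on 3 and 11 June, onset is June with no day, and the event stops on 14 June. The month matches and 3 June is not after 14 June, so onset becomes 3 June, in Period 1. Both readings give this result.

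**Literal reading.** A Period 2 event is dated to dose 1 whenever its onset falls in the month of dose 1. A month start lies between dose 1 and onset with probability 12(g + o)/366, so the misdated share is 1 − 12(g + 3.5)/366.

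| Gap (days) | Calculation | Dated to Period 1 |
|---|---|---|
| 7 | 1 − 126/366 | 65.6% |
| 8 | 1 − 138/366 | 62.3% |
| 12 | 1 − 186/366 | 49.2% |
| 14 | 1 − 210/366 | 42.6% |
| 21 | 1 − 294/366 | 19.7% |

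If onsets fall only 0 to 2 days after dose 2 (mean 1), the shares are 1 − 96/366 = 73.8% at 7 days, 1 − 108/366 = 70.5% at 8 days and 1 − 180/366 = 50.8% at 14 days.

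**Nested reading.** A Period 2 event escapes only if a new month starts between dose 2 and onset (12 × 3.5 = 42 of 366) or dose 2 is itself on the 1st (12 of 366). The misdated share is 1 − 54/366 = 85.2% at every gap, or 1 − 24/366 = 93.4% with onset within 2 days.

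**Fully missing date.** A Period 2 event with a known stop date always stops after dose 1, so it is always dated to dose 1.

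**Does SAP 10.2 catch these?** A true Period 2 event stops on or after the day of dose 2. Once dated to dose 1, it appears to run past dose 2. All the misdated Period 2 events therefore fall into the group sent to case-by-case evaluation.

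**Reverse movement, literal reading only.** Doses are on 30 June and 8 July; a Period 1 event truly starts on 5 July, is recorded as July and stops on 10 July. The months differ, so onset becomes 10 July, in Period 2. It now appears to start after dose 2, so no review is triggered. For a Period 1 event starting o days after dose 1 (o = 0 to g − 1) and lasting d days, the share moved is the sum of 12o/366 over onsets with o + d ≥ g, divided by g:

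- g = 7, d = 1: (72/366)/7 = 2.8%
- g = 8, d = 7: (336/366)/8 = 11.5%
- g = 14, d = 7: (840/366)/14 = 16.4%

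The range is about 3-16% for gaps of 7 to 14 days and durations of 1 to 7 days.

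**The case against.** The strongest reply is that a reader might infer the SAP counts these events under the wrong food treatment. It does not go that far. The case-by-case sentence in SAP 10.2 covers every misdated Period 2 event, so the outcome is unspecified rather than fixed as wrong. That stands. But the SAP gives no criteria, decision-maker or timing for the review, Part 1b is open-label, and the review would be prompted by an artificial date.

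Other stronger readings also fail:

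- **The defaults are never reached.** This holds on the literal reading only.
- **Most Period 2 events at any gap.** On the literal reading the share falls below half from a gap of about 12 days, and the washout may be adjusted.
- **A shift in one direction.** The literal reading also moves some Period 1 events to Period 2. With sequences AB and BA, the Period 2 to Period 1 shift mainly blurs the fed/fasted contrast rather than favouring one condition.
- **Harm to medication tables.** SAP 7.6 plans only a listing of medications. A medicine still taken after dosing is concomitant under SAP 6.3 whatever its start date.

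Practical reach also limits the point. Participants are resident for 48 hours after each dose, return on Days 4 and 5, and have AEs recorded continuously, so missing onset days should be rare. No inferential safety analysis is planned, and incidence over both treatments together does not depend on the period assigned.

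**Conclusion.** The point holds as a rule that produces wrong dates as written, with small expected reach. At the scheduled gap of about 7-8 days, 62-66% (literal) or 85% (nested) of Period 2 events with a missing onset day are dated to Period 1. Whether they are then counted under the wrong food condition depends on a review without criteria. Separately, the literal wording defeats its own defaults, can move Period 1 events to Period 2 unreviewed, and fails for ongoing events.

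The percentages apply only to events with a missing onset day. They rest on assumed uniform dose and onset dates, and the reverse movement also on assumed durations. The documents do not say how many partial dates to expect; the number is probably small. No effect on medication tables is shown.

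**What to change.** In SAP 6.4:

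1. Limit the stop-date clause to events whose partial date is in the same month (or year) as the dose and that stopped before dosing. In all other cases use the first of the month or 1 January.
2. For Part 1b, assign a partial-date AE to the period recorded at collection, where available. Otherwise use the latest dose in the known month or year that is not after the stop date; for a fully missing date, use the latest dose overall that is not after the stop date. Flag every event whose possible onset window includes both doses, and send it to the SAP 10.2 review.

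The cost is a few sentences and a small programming change. The review in item 2 is needed because the latest-dose rule, while it misdates no Period 2 event under the assumptions above, moves Period 1 events still ongoing at dose 2. The share is the sum of 1 − 12(g − o)/366 over Period 1 onsets with o + d ≥ g, divided by g:

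| Duration | Gap 7 days | Gap 8 days |
|---|---|---|
| 1 day | (1 − 12/366)/7 = 13.8% | 12.1% |
| 3 days | (3 − 72/366)/7 = 40.0% | 35.0% |
| 7 days | (7 − 336/366)/7 = 86.9% | 76.0% |

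Counting both periods (8 Period 2 and g Period 1 onset days, equally weighted), the latest-dose rule alone misassigns 0-19% of partial-date events lasting 0-3 days, against 31-46% under the current rule if the review changes nothing. For 7-day events it gives no clear gain (38-41% against 37-46%). It should therefore not stand without the recorded period or the review.

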7.1 Participant Disposition

The number of participants who were screened, who screen failed, who were enrolled, who were dosed, who completed the study, and who were discontinued from the study, along with reasons for discontinuation, will be summarized. The data will be presented by study part, cohort (sequence for Part 1b), and overall (frequency and the percentage of participants) and presented by participant in a data listing.

Participants who initially screen fail may be determined eligible for a rescreen. These participants will only be counted under a given cohort as screened once. If they fail the rescreen, they will also only be counted as a screen fail once.

Participants may also meet study criteria, but may not be needed for a given cohort. These will be considered screen failures. These participants may subsequently be assigned as standby to replace participants who drop out of the cohort before dosing or rescreened for another cohort. Standby participants will be considered enrolled in a cohort. Participants who rescreen into another cohort within the same study part will be counted as screened for both cohorts, but only once for the study part overall. Participants who rescreen into another cohort in another study part will be counted as screened for both cohorts and study parts.

7.2 Protocol Deviations

Participant data will be reviewed regularly throughout the study according to the protocol deviation/non-compliance plan (PDNCP). All protocol deviations will be categorized and presented by participant in a data listing.

7.3 Inclusion and Exclusion Criteria

All recorded inclusion and exclusion criteria status will be presented by participant in a data listing. Each participant's inclusion or exclusion from each analysis population will also be presented in a data listing.

This document is confidential.

7.4 Demographics and Other Baseline Characteristics

All demographics (age, sex, race, and ethnicity) and baseline body measurements (height, weight, and BMI) will be summarized by study part and treatment (sequence for Part 1b), and presented by participant in a data listing. For Parts 1a and 2, summary tables will be presented by dose (study drug and placebo) and by study drug overall. For Part 1b, summary tables will be presented by sequence and overall.

Descriptive statistics (n, mean, SD, min, median, and max) will be calculated for continuous variables using the last results obtained prior to study drug administration. Frequency counts and percentages will be tabulated for categorical and binary variables.

7.5 Medical History

Medical history will be presented by participant in a data listing. The latest version of the Medical Dictionary for Regulatory Activities (MedDRA) will be used to classify medical history terms by system organ class (SOC) and preferred term (PT). Output data will include the MedDRA version used in the study.

7.6 Medications

Medications taken by participants before dosing will be documented as prior medications and medications taken by participants after dosing until the last study day will be documented as concomitant medications. Prior and concomitant medications will be presented by participant in a data listing. The latest version of the World Health Organization Global Drug Dictionary (WHO Drug) will be used to classify medications by anatomical therapeutic chemical (ATC) classification code (2nd level) and preferred name. When 2nd level classification code is not available, 1st level classification will be used instead. Output data will include the WHO Drug version used in the study.

7.7 Drug, Cotinine, and Alcohol Screens

The results of drug, cotinine, and alcohol screens will be presented by participant in data listings.

7.8 Pregnancy Screening

Pregnancy tests will be administered to women of child-bearing potential. The follicle stimulating hormone (FSH) level will be tested in postmenopausal women. All results will be presented by participant in data listings.

7.9 Additional Screening Tests

The results of serology tests and COVID-19 tests will be presented by participant in data listings.

8. Pharmacokinetic (PK) Analyses

Phoenix[®] WinNonlin[®] software will be used for all PK analyses. Statistical analyses will be performed using SAS for Windows software.

All PK concentration and PK parameter analyses will be conducted on the PK population.

This document is confidential.

Plasma and urine concentrations of ATH-399A will be listed by participant and treatment and summarized by treatment and timepoint, using descriptive statistics, for the PK population. Individual and mean plasma concentration-versus-time profiles will be presented graphically for both linear and semi-log scale by treatment for the PK population. Descriptive statistics (n, arithmetic mean, SD, minimum, median, maximum, coefficient of variation [CV%], geometric mean and geometric CV%) of the plasma PK parameters will be provided by study part and treatment.

8.1 Data Presentation

PK concentrations will be listed and summarized by nominal sampling time and treatment. For all PK analyses, concentration values below the quantification limit (BLQ) that occur before the first measurable concentration of the study drug will be set to “0.00”; BLQ values that occur after first measurable concentration will be set to “missing”. No imputations will be made on BLQ concentrations.

Invalid concentration values (due to bioanalytical or clinical issue) that occur prior to dosing will be replaced by “0.00”. Invalid concentration values that occur after dosing will be set to “missing” for tabulation, graphical representation, and calculation purposes.

The actual clock time for dosing and the actual clock time for each PK sample collection will be recorded. For all sampling times, the actual sampling duration will be calculated as the difference between the sample collection actual clock time and the actual clock time of dosing. The actual post-dose sampling times, expressed in hours and rounded off to three decimal places, will be used to calculate the PK parameters. Pre-dose sampling times will always be reported as zero (0.000), regardless of the time difference. Nominal sampling times will be used in concentration tables and mean graphs, while actual sampling times for post-dose samples will be used in the individual graphs. Actual sampling times for post-dose samples also will be used for PK parameter derivation, unless the actual sampling time is missing, in which case, the nominal time will be used.

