 - on Day 9: pre-dose (within 2 hours of dosing),
 - on Day 10: pre-dose (within 2 hours of dosing),
 - on Day 11: pre-dose (within 2 hours of dosing),
 - on Day 12: pre-dose (within 2 hours of dosing) and 0.25 (± 2 min), 0.5 (± 2 min), 1 (± 5 min), 1.5 (± 5 min), 2 (± 5 min), 3 (± 10 min), 4 (± 10 min), 6 (± 10 min), 8 (± 10 min), 12 (± 10 min), and 16 (± 30 min) hours post-Day 12 dose and
 - on Day 13: at 24 hours (± 30 min) and 36 hours (± 30 min) post-Day 12 dose,
 - on Day 15: at 72 (± 1 hr) hours post-Day 12 dose (outpatient visit), and
 - on Day 16: at 96 (± 1 hr) hours post-Day 12 dose (outpatient visit).
10. In potential post-menopausal women only to confirm the post-menopausal status.
11. Women of childbearing potential (only) will have a urine pregnancy test at Screening and at discharge on Day 13, and a serum pregnancy test on Day -1.

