3.3.3 Part 2 (MAD)

Participants allocated to the MAD part will receive daily doses of ATH-399A, or matching placebo, under fasting conditions, for 12 consecutive days. The planned dose levels and regimens are listed below in Table 3.3-2.

Table 3.3-2: MAD Treatments

Cohort Number	Number of Participants Receiving ATH-399A	Number of Participants Receiving Placebo	Planned Dose
1	6	2	TBD mg
2	6	2	TBD mg
3	6	2	TBD mg

Each cohort will include 8 participants, 6 participants will receive ATH-399A and 2 participants will receive placebo.

Dose levels of ATH-399A will be based on data from Part 1 (Part 1a and 1b) and recommendation from the SRC. From Day 1 to Day 12, participants will receive either ATH-399A or placebo once daily (QD) for a total of twelve (12) consecutive days.

This document is confidential.

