For Part 2, plasma concentration observed before treatment administrations (C_{trough}) and during repeated dosing (Day 9, Day 10, Day 11, and Day 12) will also be presented.

Area under the concentration-time curve (AUC) parameters will be calculated using the linear up log down trapezoidal method, where the linear trapezoidal rule is used any time the concentration data are increasing and the logarithmic trapezoidal rule is used any time that the concentration data are decreasing.

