8.4 Attainment of Steady State

For Part 2, a repeated measures analysis will be carried out on natural log-transformed pre-dose concentrations (Days 9 to 12) to determine attainment of steady-state for ATH-399A. The approach is based on the comparison of natural log-transformed trough concentration values. The response variable will be the natural log-transformed pre-dose concentration and the model will include dose, visit, and dose-by-visit interaction as fixed effects and participant within dose as repeated effect. The model will be fit using restricted maximum likelihood and the Kenward-Roger degrees of freedom approximation.^b An unstructured covariance matrix will be used; if the unstructured covariance matrix fails to converge, simpler covariance matrix structures such as compound symmetry will be considered.^c

This document is confidential.

The SAS code will follow the format below. The input variables, datasets, and labels are depicted in italicized red text and have been given generic names.

```
proc mixed data=dataset;
  class dose visit participant;
  model ln_ctrough = dose visit dose*visit / ddfm=KR;
  repeated / type=un subject=participant(dose);
  lsmeans dose*visit;
run;
```

Contrasts will be tested between each dosing timepoint and the pooled mean over all outstanding dosing timepoints (i.e., Day 9 pre-dose value versus the average pre-dose value of Days 10 through 12, Day 10 pre-dose value versus the average pre-dose value of Days 11 through 12, Day 11 pre-dose value versus the pre-dose value of Day 12).

The first non-significant comparison will be concluded to be the dose number (Day x) at which steady state concentrations are attained. If the dose*time effect is found statistically significant, these contrasts will be done separately for each dose level. The p-value for difference of least-squares means (LSM) will be provided.

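### SAP 8.1 does not limit its 0.00 rule for invalid pre-dose samples to the first dose, so an invalid Part 2 trough on Days 9-12 could be recorded as zero

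*SAP*

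**What the plan says.** SAP 8.1 has two sentences on invalid concentrations. The first reads "Invalid concentration values (due to bioanalytical or clinical issue) that occur prior to dosing will be replaced by" 0.00. The second reads "Invalid concentration values that occur after dosing will be set to" missing, and it covers tables, graphs and calculations. Neither sentence names the first dose, a study part or a day. SAP 6.1 applies its descriptions to all study parts unless it says otherwise. The same section 8.1 adds: "Pre-dose sampling times will always be reported as zero (0.000), regardless of the time difference".

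Part 2 is a repeated-dose part: "Participants allocated to the MAD part will receive daily doses of ATH-399A, or matching placebo, under fasting conditions, for 12 consecutive days" (SAP 3.3.3). Protocol Table 3 schedules a sample "on Day 9: pre-dose (within 2 hours of dosing"), and likewise on Days 10, 11 and 12. These samples are used in three ways:

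- **Trough presentation.** SAP 8.2.3 begins "For Part 2, plasma concentration observed before treatment administrations" and reports these values as C_trough for Days 9 to 12.
- **Steady-state model.** SAP 8.4: "The response variable will be the natural log-transformed pre-dose concentration".
- **Day 12 interval.** The Day 12 pre-dose sample is time zero of the interval from which AUC0-tau and C_min are taken.

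Two other rules bear on the point. SAP 6.4 allows only observed concentrations into the PK analysis, with values below the quantification limit (BLQ) as the sole exception. SAP 8.1 sets a BLQ value to zero only before the first measurable concentration, and to missing after it.

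**The concern.** Zero is a sensible stand-in for a failed assay only when the participant has had no drug. By Day 9 of Part 2 a participant on active drug has had eight daily doses, so a failed assay leaves the trough unknown. The readable text gives no half-life. That drug is on board is inferred from daily dosing, from the planned log-scale trough analysis, and from protocol 9.7, which expects steady state to have been reached when sentinel participants are assessed at least 96 hours after Day 1.

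A literal application would also put the SAP's rules out of order. A Day 9 sample that was measured and found BLQ, after earlier measurable values, becomes missing. A Day 9 sample that could not be measured at all becomes zero.

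At stake are the trough tables and mean graphs for the affected day and, if Day 12 is the affected day, that participant's C_min, which is a Part 2 secondary endpoint.

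**Working it through.** The plan gives no figure of its own here. The check has two steps: does the rule reach these samples, and what changes if it does?

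**1. Reach of the rule**

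| Text | Sense of dosing |
|---|---|
| SAP 8.1, pre-dose times reported as zero | Each dose: the Day 12 pre-dose sample can be time zero only relative to the Day 12 dose |
| Protocol Table 3, Day 9 sample | That day's dose |
| SAP 6.3 and 7.6, prior and concomitant medication | Start of treatment |
| SAP 6.3 and 10.2, baseline and treatment-emergent events | The first dose is named explicitly |

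The per-dose sense, which is the one used within 8.1, brings Days 9 to 12 under the zero rule. The start-of-treatment sense brings them under the rule that sets values to missing.

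**2. Size if zero is applied**

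From SAP 3.3.3: 6 active participants per cohort and three cohorts.

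*Trough summary, equal troughs of 10 (illustrative).*

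- Mean with one zero = (5 × 10 + 0)/6 = 8.33, against 10 for the five valid values. The change is −1/6 = −16.7%.
- SD = √[(5 × 1.667² + 8.333²)/5] = √16.67 = 4.08.
- CV = 4.08/8.33 = 49%, against 0% with the value set to missing. The minimum is 0.

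*Trough summary, unequal troughs.* The between-participant CV is not in the documents, so 20% to 50% is assumed, with log-normal values and 20,000 simulated sets of 6.

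| Assumed true CV | Mean observed CV, value missing (n = 5) | Mean observed CV, value 0.00 (n = 6) |
|---|---|---|
| 20% | 19% | 53% |
| 30% | 27% | 58% |
| 50% | 43% | 69% |

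*Steady-state model.* ln(0) is undefined. The record most likely drops out, which is also what happens to a missing value. The contrasts are then the same either way, and only the trough table (n = 6) and the model (n = 5) disagree.

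*Day 12 C_min.* If the zero is carried in, C_min = 0. SAP section 8 specifies a geometric mean and geometric CV for PK parameters, and a zero cannot enter them. SAP 8.3 also fits C_min ss on the log scale. That model is one regression across dose levels, so the loss is one of up to 3 × 6 = 18 active values. It runs only if there are at least three different treatments, and the Part 2 doses are still to be determined.

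*Day 12 AUC0-tau.* Only the 0 to 0.25 h trapezoid changes. The loss is about (0.25/2) × C(0) = 0.125 × C(0). With AUC0-tau = 24 × average concentration, the relative loss is (0.125/24) × C(0)/average = 0.52% × C(0)/average. It therefore stays below about 0.52% when the trough is below the average. A one-compartment calculation on the protocol sampling times, with an assumed absorption rate of 1.5/h, gives:

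| Assumed half-life | Change in AUC0-tau |
|---|---|
| 6 h | −0.10% |
| 12 h | −0.25% |
| 24 h | −0.37% |
| 48 h | −0.44% |

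The Day 12/Day 1 AUC ratio for that participant moves by the same small percentage.

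**The case against.** The strongest reply is that the SAP may already do the right thing. A Day 9 trough precedes that day's dose but follows eight others, so it fits the sentence on values after dosing. SAP 6.3 and 7.6 use dosing for the start of treatment, and SAP 6.4 argues against inserting any value that was not observed. On that reading invalid troughs are already missing and there is no error. This stands as far as it goes: the text does not unambiguously order a zero. It does not remove the point, because 8.1 itself uses the per-dose sense, and two programmers could treat the same sample differently.

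Second, C_min is defined in SAP 8.2.3 as an observed minimum, and a replacement value is not observed. That is fair, which is why C_min could become zero rather than must.

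Third, harm needs an invalid sample in the first place. The documents give no rate. There are 3 × 6 × 4 = 72 active-arm samples from Days 9 to 12. If 0.5%, 1% or 2% were invalid, independently (assumed rates), the chance of at least one, 1 − (1 − p)^72, is about 30%, 52% or 77%. The event is plausible but not certain.

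Fourth, the outputs are secondary and descriptive, the study is not powered for significance, and individual concentrations are listed. All of that stands and sets the severity.

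**Conclusion.** The rule is worded too broadly. Read literally, it can write a false zero into a Part 2 trough, against the SAP's own rule on observed data. The size is a fall of about 17% in one cohort's arithmetic mean trough on one day per invalid sample (6 active participants with similar values assumed), a minimum of 0, an inflated SD and CV, and possibly one C_min of zero. The severity is minor.

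A reader might infer more than the documents support:

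- **That the steady-state conclusion would be wrong.** If ln(0) simply drops out, the analysis is the same as with missing.
- **That the geometric mean trough could not be computed.** Geometric means are specified for PK parameters. Concentrations get descriptive statistics, whose default list in SAP 6.2 contains no geometric mean, and C_trough is not in the Part 2 parameter table. The point applies only to C_min.
- **That one value in six is lost from the power model.** It is one of up to 18, and only if the model is run.
- **That exposure or accumulation results would be distorted.** AUC0-tau moves by 0.10% to 0.44% over the assumed half-lives of 6 to 48 h.

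**What to change.** In SAP 8.1:

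- Limit the 0.00 replacement to invalid samples taken before the participant's first dose of study drug.
- State how an invalid Part 1b Period 2 pre-dose sample is handled. It follows the Period 1 dose, and the washout of at least 7 days may be adjusted on Part 1a PK data (protocol 7.1.2), so the same ambiguity arises there.
- Set invalid Part 2 pre-dose values on Days 9 to 12 to missing in tables, graphs, C_min and models.

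The cost is a sentence or two in the SAP and the matching programming note. No design change or new data are needed. After the change, the trough summary for an affected day rests on the 5 valid values, and its expected mean is not shifted by an artificial zero.
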